9.4.7. Safety Analyses

The number and the percentage of patients experiencing adverse events, adverse drug reactions, serious adverse events, severe adverse events and adverse events leading to study withdrawal will

be summarized by treatment group. Adverse events will also be summarized by System Organ Class (SOC) and Preferred Term (PT) using the Medical Dictionary for Regulatory Activities (MedDRA) dictionary and comparison between treatments will be performed using a Chi-square test or Fisher's exact test, as appropriate.

Any other safety variables to be summarized by treatment group using descriptive statistics will be detailed in the SAP.

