8.3.8. Pregnancy

Any pregnancy where the fetus may have been exposed to study drug, should be notified by the Investigator to the Sponsor, by filling in the "Pregnancy Form" and sending it, within 24 hours of its knowledge, to the Sponsor:

- by e-mail ([contact])
- Outcome of the pregnancy (normal or abnormal) must be followed up and recorded.
- Abnormal pregnancy outcome must be notified on an expedited basis (i.e. within 24 hours of the Investigator becoming aware of the abnormal pregnancy outcome) using the SAE form. This refers especially to congenital anomalies in the fetus/child, fetal death and spontaneous abortion, and adverse reactions in the neonate that are classified as serious.
- Pregnancy will be recorded as an AE in all cases. It will be qualified as an SAE only if it fulfils SAE criteria (see above).

8.3.9. Disease Related Events and/or Disease Related Outcomes not Qualifying as AEs or SAEs

Not applicable

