9.2. Sample Size Determination

The sample size calculation is based on the superiority criteria of the LABD+ICS group vs. LABD alone group in terms of re-hospitalization and/or death. With 464 patients in each group, the percentage of patients experiencing the composite event (re-hospitalization and/or death) is expected to be 9% in the LABD+ICS group and 15% in the LABD alone group. A log-rank test (two-sided 5% significance level) will have 80% power to detect a difference between treatment groups in terms of time to first re-hospitalization and/or death (primary efficacy endpoint). Adjusting for an expected 10% dropout rate, a total of 516 patients per group will need to be randomized.

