
c. Requires inpatient hospitalization or prolongation of existing hospitalization
 
In general, hospitalization signifies that the participant has been detained (usually involving at least an overnight stay) at the hospital or emergency ward for observation and/or treatment that would not have been appropriate in the physician's office or outpatient setting. Complications that occur during hospitalization are AEs. If a complication prolongs hospitalization or fulfills any other serious criteria, the event is serious. When in doubt as to whether "hospitalization" occurred or was necessary, the AE should be considered serious.
 
Hospitalization for elective treatment of a pre-existing condition that did not worsen from baseline is not considered an AE.

d. Results in persistent disability/incapacity
 
 • The term disability means a substantial disruption of a person's ability to conduct normal life functions. • This definition is not intended to include experiences of relatively minor medical significance such as uncomplicated headache, nausea, vomiting, diarrhea, influenza, and accidental trauma (eg, sprained ankle) which may interfere with or prevent everyday life functions but do not constitute a substantial disruption.

e. Is a congenital anomaly/birth defect**f. Important medical event**

- Medical or scientific judgment should be exercised in deciding whether SAE reporting is appropriate in other situations such as important medical events that may not be immediately life-threatening or result in death or hospitalization but may jeopardize the participant or may require medical or surgical intervention to prevent one of the other outcomes listed in the above definition. These events should usually be considered serious.

Examples of such events include invasive or malignant cancers, intensive treatment in an emergency room or at home for allergic bronchospasm, blood dyscrasias or convulsions that do not result in hospitalization, or development of drug dependency or drug abuse.

SAE not requiring immediate reporting

The following reasons for hospitalisations will not to be managed as SAEs but just recorded in the CRF:

- Hospitalization planned before entry into the clinical study which is part of the normal treatment or monitoring of the studied indication and not associated with any deterioration in condition;

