8.1 Adverse events

Definitions and data conventions

Pre-treatment adverse events

An AE will be classified as pre-treatment AE if it starts before the date of randomization (AE onset date < date of randomization).

Treatment-emergent adverse event (TEAE)

An AE will be classified as a TEAE if it starts on or after the date of randomization (AE onset date \geq date of randomization).

In case of missing or incomplete dates not allowing a direct allocation to any of the two categories of AEs, a worst-case allocation will be done according to the available parts of the onset and the end dates. The AE will be allocated to the first category allowed by the available data, according to the following order:

- TEAE
- Pre-treatment.

Serious adverse event (SAE)

A SAE is an AE judged as serious.

Adverse drug reaction (ADR)

An ADR is an AE with relationship to study treatment equal to “Yes”.

Severe adverse event (SAE)

A SAE is an AE judged as severe intensity.

Adverse event leading to study withdrawal

An AE leading to study withdrawal is an AE with action taken equal to “Drug withdrawn” or “Drug interrupted”.

Count of adverse events

Two AEs with the same Preferred Term (PT) and classified in the same category (pre-treatment AE or TEAE) will be considered as two different events when calculating the “number of events” in the tables.

Statistical analysis

Pre-treatment AEs and TEAEs will be presented separately. Pre-treatment AEs will be presented in the listings only.

The number of treatment-emergent AEs, SAEs, ADRs, severe AEs and AEs leading to discontinuation, and the number and the percentage of patients experiencing treatment-emergent AEs, SAEs, ADRs, severe AEs and AEs leading to discontinuation will be summarised by treatment group. Differences between groups will be evaluated using Chi-square test or Fisher’s exact test (if more than 20% of the cells in a contingency table have expected counts less than 5).

Title	Statistical Analysis Plan Template		
-------	------------------------------------	--	--

Code	Version	Effective Date	Page
FRM_ST03_032	02	02 Oct 2017	24 of 26

AEs will be coded using the MedDRA dictionary (version 21.0). The SOCs and PTs will be used for tabulation. The number of treatment-emergent AEs and the number and the percentage of patients with at least one treatment-emergent AE will also be presented by SOC and PT by treatment group.

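### SAEs are compared between arms only as one any-SAE total that contains the primary events, so a fall in COPD admissions can offset a rise in other serious events; SAEs should also be shown by type

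*Protocol*

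**What the plan says.** **What counts as an SAE.** Protocol Appendix 3 (10.3) makes any death serious, and any event that "Requires inpatient hospitalization or prolongation of existing hospitalization". The same appendix exempts planned, routine or elective stays without deterioration. Protocol 8.3.9, headed "Disease Related Events and/or Disease Related Outcomes not Qualifying as AEs or SAEs", is marked not applicable, so COPD exacerbations are not taken out of AE or SAE reporting.

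**The primary endpoint.** Protocol section 3 defines it as time to first re-hospitalisation or death from any cause. SAP 7.1 takes the re-hospitalisations from the COPD Exacerbation Form and adds deaths.

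**The SAE analysis.** Protocol 9.4.7 plans, by treatment group, "The number and the percentage of patients experiencing adverse events, adverse drug reactions, serious adverse events" and further AE categories. SAP 8.1 gives the number of SAEs and the number and percentage of patients with one, and tests the difference by chi-square or Fisher's exact test. For the breakdown by type it says that "the number and the percentage of patients with at least one treatment-emergent AE will also be presented by SOC and PT by treatment group". That table is for all treatment-emergent AEs. Neither document plans a table of SAEs by SOC and PT, or an SAE summary that sets COPD exacerbations apart.

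**What exists alongside.** SAP 7.2 compares pneumonia events and acute cardiac events by Poisson regression and tabulates deaths as cardiovascular or other. SAP 8.1 also tests ADRs, severe AEs and AEs leading to discontinuation.

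**The concern.** In this trial a treatment that works as hoped also lowers the number of SAEs, because the events it prevents are themselves SAEs. A lower SAE total in the LABD+ICS arm would then partly restate the efficacy result. It would say little about whether other serious events became more or less frequent.

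The total adds together two components that may move in opposite directions: COPD admissions, which are expected to fall, and all other serious events, which may rise. When only the sum is compared, a rise in the second can be cancelled by a fall in the first. The SOC/PT tables do not resolve this, because a row that mixes serious and non-serious events does not show how many of each kind were serious in each arm. At stake is what the report can say about serious harm by type. The primary analysis and the sample size are not affected.

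**Working it through.** **1. Reproduce the design figure.** Protocol 9.2 states: "With 464 patients in each group", event rates "expected to be 9% in the LABD+ICS group and 15% in the LABD alone group", and "A log-rank test (two-sided 5% significance level) will have 80% power".
- Hazard ratio under proportional hazards: ln(0.91)/ln(0.85) = 0.580.
- Freedman events: (1.960 + 0.842)² × [(1 + 0.580)/(1 − 0.580)]² ≈ 111.3.
- Per arm: 111.3/(0.15 + 0.09) = 463.7, or 464. Dropout: 464/0.90 = 515.6, or 516.

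Both stated sizes are reproduced. The documents give no expected SAE rates.

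**2. How far the primary effect alone moves the SAE total.** Suppose every primary event is an SAE and there are no other SAEs.
- 464 per arm: 0.15 × 464 ≈ 70 and 0.09 × 464 ≈ 42. Uncorrected chi-square 7.96, p = 0.005, in favour of ICS.
- 516 per arm: 77 vs 46. Chi-square 8.87, p = 0.003.
- If 5% to 20% of primary hospitalisations were exempt elective stays (assumption), this component would be 14.3% vs 8.6% down to 12.0% vs 7.2%.

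This is a limiting case that shows the direction of the pull. It does not predict the SAE table.

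**3. Offsetting within the total.** All rates here are assumed, LABD vs LABD+ICS. Let a be the risk of a COPD SAE and b the risk of any other SAE, taken as independent: any SAE = 1 − (1 − a)(1 − b). Power uses z = |difference|/SE − 1.96, with SE = √[(p₁(1−p₁) + p₂(1−p₂))/516].

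| COPD SAE | Other SAE | Any SAE | Chance total is significant | Power for other SAE |
|---|---|---|---|---|
| 10% vs 5% | 6% vs 9% | 15.4% vs 13.6% | 13% | 45% |
| 10% vs 5% | 6% vs 10% | 15.4% vs 14.5% | 6% | 66% |

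First row: 1 − 0.90 × 0.94 = 0.154 and 1 − 0.95 × 0.91 = 0.1355. For other SAEs, SE = 0.0164, so the expected difference is 3.0 points with a 95% CI of about −0.2 to 6.2. Total and component point in opposite directions.

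**4. A second construction.** Take 464 per arm, primary events at the design rates, and an assumed further serious harm of 2% vs 5% in patients without a primary event.
- Total: 17% vs 14% (79 vs 65 patients), p = 0.20, leaning towards ICS.
- Separate contrast: 9 vs 23 patients, p = 0.012, against ICS.
- Other assumed harms (1% vs 3%, 2% vs 4%, 3% vs 6%): total p from 0.08 to 0.22, always leaning towards ICS; separate p from 0.027 to 0.055.
- Power of the separate contrast across these four cases: 43% to 70%.

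Steps 2 and 3 rest on different premises and should not be combined. Step 2 treats SAEs as nothing but primary events; step 3 lets other SAEs differ between arms.

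**The case against.** **A reader might infer that the SAE comparison simply repeats the primary endpoint.** The documents do not support that. The inclusion runs one way: primary events are SAEs, but not all SAEs are primary events. SAEs also include life-threatening, disabling or medically important events without admission. They are reviewed to Visit 7, whereas the primary endpoint is censored at Visit 6 or withdrawal. They are analysed in the safety population by treatment received, whereas the primary analysis uses ITT by randomised arm. Under SAP 7.1, where re-hospitalisations come from the COPD Exacerbation Form, the SAE total is broader still.

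**A reader might infer that the plan as a whole can hide a harm of ICS.** That is also too strong. Pneumonia, the ICS harm that the protocol names, has its own rate ratio with CI and p-value, and so do acute cardiac events. Deaths are split by cause, all treatment-emergent AEs are shown by SOC and PT, and the Data Monitoring Committee reviews safety data. Moreover, under the protocol's all-cause definition a non-COPD admission is itself a primary event, so the primary result would already net that harm against the benefit. Offsetting within the SAE total matters most under the SAP's derivation, or for serious events without admission.

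**A reader might infer an undeclared change from the protocol**, because Protocol 9.4.7 mentions a between-treatment comparison in the same sentence as SOC and PT, while SAP 8.1 only presents those rows and SAP 4.8 lists no such change. The protocol sentence can equally attach the comparison to the overall counts, so this is not established.

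It is also fair that the offsetting rates are assumed, that a separate contrast would often miss a harm of this size, and that unblinded investigators assign the cause of admission. These points limit the claim and the weight of any added contrast. They do not remove the omission: no planned summary shows serious events by type and arm.

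**Conclusion.** The point holds in limited form. Apart from exempt stays, primary events are a subset of SAEs, and the only SAE contrast is an any-SAE total. That total will lean towards ICS if ICS works as planned, and it can offset an increase in other serious events. In the assumed examples, an excess of 3 to 4 percentage points in other SAEs leaves the total at 15.4% vs 13.6% or 15.4% vs 14.5%, still nominally in favour of ICS.

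This rests on assumed SAE rates, on independence of the two components (step 3) or disjoint patients (step 4), and on full reporting of COPD admissions as SAEs. In these examples a significant SAE advantage is unlikely; the risk is a reassuring total that says little about the components. The gap is confined to serious events by type, and closing it is a cheap improvement to safety reporting.

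**What to change.** In SAP 8.1:

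1. Add a table of treatment-emergent SAEs by SOC and PT by arm, with numbers of events and numbers and percentages of patients, in the same layout as the table for all treatment-emergent AEs.
2. Beside the all-SAE comparison, show patients with at least one SAE other than a COPD exacerbation by arm, with the difference and 95% CI. Identify COPD exacerbations from the coded SAE term, using a list of PTs fixed before the data review.

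Keep the all-SAE total, because it does not depend on attribution of cause by unblinded investigators. Label the added contrast descriptive, since its power is modest (43% to 70% in the assumed cases). SAE reports and MedDRA coding are already planned, so the cost is two further summaries and one short term list. Sample size, primary analysis and data collection do not change.

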6.3. Measures to Minimize Bias: Randomization and Blinding

All participants will be centrally assigned to randomized study intervention using an Interactive Web Response System (IWRS). Before the study is initiated, the log in information and instructions for the IWRS will be provided to each site.

The center will be considered as a unique stratifying factor, so the randomization will follow a balanced-block center-stratified design.

Study intervention will be dispensed at the study visits summarized in the SoA.

This is an open-label study; however, the specific intervention to be taken by a participant will be assigned using an IWRS. The site will contact the IWRS prior to the start of study intervention

administration for each participant. The site will record the intervention assignment on the applicable case report form.

Potential bias will be reduced by using central randomization.

Since this is an open label study, no unblinding procedures are foreseen.

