4.4 Covariates

All the analysis of covariance (ANCOVA) models will include the baseline value of the variable and age as quantitative independent variables, treatment group and centre as qualitative independent variables.

The Poisson regression model and the Cox proportional hazards model will include center and treatment group as qualitative independent variables and age as quantitative independent variable.

The baseline to be considered in the statistical analysis for each variable is reported in the table below:

Endpoint	Baseline
Spirometry	Visit 2 (randomization)
COPD Assessment test (CAT)	Visit 2 (randomization)
mMRC dyspnea scale	Visit 2 (randomization)
Height and weight	Visit 1 (screening)
Physical examination	Visit 1 (screening)
Laboratory assessments	Visit 1 (screening)
12-lead ECG	Visit 1 (screening)
Vital signs (blood pressure and heart rate)	Visit 2 (randomization)

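### The overall adverse-event comparisons ignore centre, the only randomisation stratum, and give a p-value without a between-arm estimate and confidence interval

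*Protocol*

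**What the plan says.** Protocol 6.3 states that "the randomization will follow a balanced-block center-stratified design", with centre as the sole stratifying factor. The synopsis plans 39 centres.

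The efficacy tests follow that design. The primary log-rank test is stratified by centre (Protocol 9.4.6, SAP 7.1). SAP 4.4 adds: "The Poisson regression model and the Cox proportional hazards model will include center and treatment group as qualitative independent variables". The ANCOVA models in the same section also contain centre.

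The safety tests do not. Protocol 9.4.7 tabulates "The number and the percentage of patients experiencing adverse events, adverse drug reactions, serious adverse events, severe adverse events" and AE withdrawals by arm, and states that "comparison between treatments will be performed using a Chi-square test or" Fisher's exact test. SAP 8.1 says: "Differences between groups will be evaluated using Chi-square test or" Fisher's exact test, the latter when too many expected cell counts are small. Neither section mentions centre, a risk difference, a risk ratio or a confidence interval.

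The two documents attach the test to different tables. In the protocol it stands in the sentence on system organ class (SOC) and preferred term (PT). In the SAP it follows the overall categories, and the SOC/PT table is only shown: patients with "at least one treatment-emergent AE will also be presented by SOC and PT by treatment group". SAP 4.8 does not list this as a change.

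Two harms are handled separately. Pneumonia and acute cardiac events are counted from adverse events (SAP 7.2) and analysed by a Poisson model with centre, which yields an adjusted rate ratio with a 95% CI.

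**The concern.** Blocking within centre balances the arms inside each centre, so differences in AE rates between centres cancel out of the treatment difference. An unstratified test still counts that variation in its standard error. The test is then too cautious, and in a safety comparison that means some excess risk goes undetected.

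Centre variation is plausible. The trial is open label, AEs are elicited by local staff with open questions (Protocol 8.3.4), and each investigator chooses the products.

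The second gap needs no assumption about centres. A non-significant p-value for SAEs puts no upper limit on the excess that the data still allow. A confidence interval does, and the plan provides one for the hazard ratio and the rate ratios but not for these categories.

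**Working it through.** **Plan's own figures.** The documents state no power or event rate for the AE tests. The stated sample size reproduces and fixes the number per arm. For 15% versus 9% at two-sided 5% and 80% power, the two-proportion formula gives 460 per arm, and 464 gives 80.4% power. By Freedman's log-rank formula, HR = ln(0.91)/ln(0.85) = 0.580 needs 112 events, and 112/0.24 = 467 per arm. With dropout, 464/0.90 = 515.6, so 516 per arm, 1,032 in total and 1,032/39 = about 26 per centre.

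**Formula.** Let p be the mean AE rate and ICC = SD²/(p(1−p)), where SD is the between-centre standard deviation of the AE rate. With 1:1 blocking within centre, the true variance of the difference is about 2p(1−p)(1−ICC)/n per-arm patients. The crude test uses 2p(1−p)/n. Hence Z(crude) ≈ √(1−ICC) × Z(stratified), and

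- real size = 2 × [1 − Φ(1.96/√(1−ICC))]
- crude power when the stratified test has 80% = Φ(1.960 + 0.842 − 1.96/√(1−ICC))

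Example at ICC 0.10: 1.96/√0.90 = 2.066, so size = 3.9% and power = Φ(2.802 − 2.066) = Φ(0.736) = 76.9%.

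| Assumed ICC | Size of crude test | Crude power (stratified = 80%) | Points lost |
|---|---|---|---|
| 0 | 5.0% | 80.0% | 0 |
| 0.01 | 4.9% | 79.7% | 0.3 |
| 0.02 | 4.8% | 79.4% | 0.6 |
| 0.05 | 4.4% | 78.5% | 1.5 |
| 0.10 | 3.9% | 76.9% | 3.1 |
| 0.20 | 2.8% | 72.9% | 7.1 |

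**Simulation check.** Assumptions: 39 equal centres, 1,032 patients, blocks of 4, Beta-distributed centre rates, mean AE rates of 5%, 15%, 30% and 60%, 20,000 trials per setting. The documents give none of the ICCs, AE rates, block size or centre sizes.

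| ICC | Crude chi-square, size | Power gained with Cochran-Mantel-Haenszel (CMH) |
|---|---|---|
| 0 | 4.9–5.1% | about 0 |
| 0.05 | 4.4–4.8% | 1.2–1.4 points |
| 0.10 | 3.9–4.1% | 2.4–2.7 points |
| 0.20 | 2.8–3.0% | 5–6 points |

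The size of the CMH test was 4.8–5.3% throughout. A separate run with 13 patients per arm in each centre, 50% incidence, SD 0.10 (ICC = 0.01/0.25 = 0.04) and odds ratio 1.4 gave 72% power crude and 74% stratified. That is where the upper limit of about 2 points at a low ICC comes from.

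**What an interval would show.** The half-width of an unstratified 95% CI for the risk difference is 1.96 × √(2p(1−p)/516):

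| AE rate in each arm | Half-width |
|---|---|
| 5% | 2.7 points |
| 15% | 4.4 points |
| 30% | 5.6 points |
| 60% | 6.0 points |

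At a 15% rate, an observed difference of zero would therefore still be compatible with an excess of up to about 4.4 points. The p-value alone does not convey that.

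**The case against.** The strongest defence is that crude chi-square and Fisher tests are a simple and valid screen for AE tables. Ignoring centre can only make them conservative, never liberal. Common seriousness criteria (Protocol Appendix 3) and example questions for all sites (8.3.4) should make AE ascertainment more uniform. All of this stands, and it is why the point concerns efficiency and reporting, not validity.

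A reader might infer that the safety tests are over-conservative as a matter of fact. The documents do not support that, because the effect vanishes if centres do not differ. Large losses need large spreads. At 50% incidence and odds ratio 1.4, an SD of 0.20 or 0.25 (ICC 0.16 or 0.25) gives 62% versus 69% or 52% versus 64% power. Under a Beta distribution, an SD of 0.25 puts the central 95% of true centre rates between about 6% and 94%, and nothing in the plan suggests such a spread.

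A reader might also infer that the plan gives no estimate of harm. It does: percentages by arm are shown, so a crude difference can be read off. Pneumonia, the ICS risk named in the objectives, and acute cardiac events have centre-adjusted rate ratios with CIs.

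Finally, a 39-stratum test suits rare preferred terms poorly, since most strata would contribute nothing. That objection is right and limits the fix to the overall categories.

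**Conclusion.** The point holds in limited form. For the overall AE, SAE, adverse drug reaction, severe-AE and AE-withdrawal categories, the analysis departs from the stratified design without a stated reason and gives no between-arm estimate with a CI.

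The missing interval is the firmer part, because it follows from the text alone. The conservatism is conditional on the ICC. At 0.05 or below it is negligible to small, with at most about 2 power points lost. A material loss, about 3 to 7 points, needs an ICC of about 0.10 to 0.20, a figure that the documents neither give nor imply. The calculation also assumes near-equal arms within centres.

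Importance is minor to moderate. The safety analysis is not invalid as planned, and the pneumonia and acute cardiac event analyses are not touched.

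**What to change.** In Protocol 9.4.7 and SAP 8.1, for the overall AE categories only:

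- report the centre-stratified Mantel-Haenszel risk difference (LABD+ICS minus LABD) with its 95% CI;
- replace the unstratified test with a centre-stratified CMH test, or an exact stratified test when events are sparse;
- keep the crude counts and percentages by arm.

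Leave the SOC/PT tables descriptive or with the simple test, and state in both documents which tables carry a test. If the difference from the protocol stays, list it in SAP 4.8.

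The cost is SAP wording and a few options in PROC FREQ, with no patients and no new data. If centres do not differ, the stratified test performs like the crude one. The small downside is that centres with one arm only, or with no events, add nothing to the stratified test. This matters somewhat more because SAP 4.5 foresees no pooling of sites.
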